8. PHARMACODYNAMICS EVALUATION

All model-based primary and secondary PD analyses will adjust for a subset of the following covariates: sex, weight group (<20 kg or \geq 20 kg), receipt of IV artesunate or artemisinin-based therapy before enrollment, and receipt of concomitant medications. Where appropriate, primary and secondary PD analyses may also adjust for receipt of oral ACT. Exploratory boxplots and stacked bar graphs of response variables by covariate values, and by timepoint when appropriate, will inform covariate selection for each model.

Primary and secondary analyses will be performed using the Pharmacodynamics Analysis Population, and a sensitivity analysis will be performed for each primary and secondary analysis including only participants who did not receive IV artesunate or other artemisinin-based therapy before enrollment.

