Exploratory scatterplots of each continuous primary outcome response variable will be presented by exposure parameter and timepoint beginning in [Figure 2](#) and continuing through [Figure 11](#) for the PD Analysis Population. Exploratory box plots of BCS will be presented by exposure parameter and timepoint in [Figure 12](#). Summary statistics for each continuous marker of physiological dysfunction and its change from baseline will also be presented by parameter and timepoint in [Table 13](#) for participants in the PD Analysis Population and in [Table 14](#) for the subset of the PD Analysis Population with no IV artesunate or other artemisinin-based therapy before enrollment. Proportions of participants with each BCS value will be presented by timepoint in [Table 15](#) for participants in the PD Analysis Population and in [Table 16](#) for the subset of the PD Analysis Population with no IV artesunate or other artemisinin-based therapy before enrollment.

Regression models will be fit to characterize the relationship between each primary outcome response and each exposure parameter at each of the above timepoints, controlling for covariates (given in Section 6.4). Note that receipt of oral ACT will only be considered for inclusion in analyses of the primary outcome

response variables at time of first hospital discharge. Exploratory boxplots of each continuous primary outcome response variable will be presented by covariate and timepoint beginning in [Figure 13](#) and continuing through [Figure 22](#). Exploratory stacked bar charts of BCS will be presented by covariate and timepoint in [Figure 23](#). These exploratory plots, presented for the PD Analysis Population, will be used to inform what subset of covariates will be included in each model.

Proportional odds mixed effects models will be used to assess the relationship between each exposure parameter and ordinal BCS at each timepoint. The proportional odds mixed effect model for BCS at any one of the four timepoints considered is defined as follows:

$$\text{logit}\{\tau_k(P_i, t_i, BCS_{0,i}, X_i)\} = \alpha_k + \beta_1 P_i + \beta_2 t_i + \eta^T X_i + BCS_{0,i} + b_i.$$

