## Mean and Standard Deviation of EC50, for example ##
mean(fit_param$ec50)
sd(fit_param$ec50)
```

Exploratory scatterplots for the response outcome measure at each timepoint given the exposure measure will be utilized to assess whether a log-transformation of the response variable may be necessary. These exploratory scatterplots as well as goodness of fit diagnostic plots will be used to assess reasonableness of model assumptions. If Emax model assumptions seem unlikely to hold, linear or polynomial models will be considered as informed by the exploratory scatterplots.

A linear model for primary outcome effect, E_i , is defined as follows:

$$E_i = E_{0,i} + \beta P_i + \eta^T X_i + e_i,$$

where E_i represents the given response outcome measure for the i th participant at the given timepoint, $E_{0,i}$ is the baseline response outcome measure for participant i , P_i is the exposure parameter value for participant i , X_i are the values of the additional covariates included in the model, and e_i are the measurement errors for participant i . These measurement errors are assumed to be independent and normally distributed with mean zero and nonzero variance. In addition to the covariates listed in Section 6.4, actual time of response measurement post-first dose will also be considered for inclusion in the model.

If linear models are fit for a primary outcome effect, the following pseudocode will be used for model fitting and to extract p-values for the exposure model parameter.

```
/* Linear model fit and output p-values */
proc glm data=dataset(where=(population=p and response=r));
*catvar = any categorical covariates included in the model;
*refvalues = the value(s) to be used as the reference level for categorical
covariate(s);
class catvar(ref=refvalues);
*baseresp = response at baseline;
*othercovars = any other covariates (including those specified in the class statement)
included in the model;
model resp = baseresp exposure othercovars / noint ss3;
by timepoint;
ods output ModelAnova=tests3;
run;
data tests3; set tests3(where=(source='EXPOSURE')) ;
rename ProbF=pval;
run;
```

A polynomial model for primary outcome effect, E_i , is defined as follows:

$$E_i = E_{0,i} + \sum_{j=1}^a \beta_j P_i^j + \eta^T X_i + e_i,$$

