where E_i represents the given response outcome measure for the i th participant at the given timepoint, $E_{0,i}$ is the baseline response outcome measure for participant i , P_i is the exposure parameter value for participant i , a is the highest order exponent included in the model with its selection informed by exploratory data plots, X_i are the values of the additional covariates included in the model, and e_i are the measurement errors for participant i . These measurement errors are assumed to be independent and normally distributed with mean zero and nonzero variance. Again, in addition to the covariates listed in Section 6.4, actual time of response measurement post-first dose will also be considered for inclusion in the model. Estimated log-likelihood statistics or other model fit statistics may be used to assist in covariate selection for linear or polynomial models.

If linear models are fit for a primary outcome effect, the following pseudocode will be used for model fitting and to extract p-values for the exposure model parameter.

```
/* Polynomial model fit and output p-values */
data dataset; set dataset;
```

```

*exposure^j from 2 up to a will be calculated;
exposurea=exposure**a;
exposurea_1=exposure** (a-1);...
run;
proc glm data=dataset(where=(population=p and response=r));
*catvar = any categorical covariates included in the model;
*refvalues = the value(s) to be used as the reference level for categorical
covariate(s);
class catvar(ref=refvalues);
*exposure... exposurea: exposure raised to the powers 1 up to a will be included as
covariates in the model;
*baseresp = response at baseline;
*othercovars = any other covariates (including those specified in the class statement)
included in the model;
model resp = baseresp exposure... exposurea othercovars / noint ss3;
by timepoint;
ods output ModelAnova=tests3;
run;
data tests3; set tests3(where=(source='exposurea'));
rename ProbF=pval;
run;

```

Model assumptions, including normality of participant-specific measurement errors, will be assessed via exploratory scatterplots and residual plots, which will also inform whether a log-transformation of the response variable may be necessary. In the event that model assumptions are not met, additional models or transformations of the response variables will be assessed, and any changes from the analyses described in this SAP will be fully described in the interim CSR.

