Models fit for the sensitivity analysis of the primary analysis using the subset of the PD Analysis Population who did not receive IV artesunate or other artemisinin-based therapy before enrollment will be of the same form as those fit in the primary analysis for the respective PD response variable, exposure parameter, and timepoint. Covariates included in each model fit for this sensitivity analysis will be those included in the respective primary analysis model with effects that remain estimable in the sensitivity analysis subset. The type of model, covariates included, and any transformations applied to the response outcome measure for each final primary analysis model will be presented in [Table 19](#) by marker of physiological dysfunction, PK exposure parameter, and timepoint for the PD Analysis Population and the subset of the PD Analysis Population that did not receive IV artesunate or other artemisinin-based therapy before enrollment.

For each model fit, the relationship between the response outcome measure at the given timepoint and the exposure measure will be assessed via a hypothesis test. If an Emax model is fit for the response outcome measure and exposure parameter, the following null hypothesis will be tested:

$$H_0: EC_{50} = 0.$$

Post-hoc distributional assessments will be performed for EC_{50} , and EC_{50} will be transformed if necessary to have an approximately normal distribution for inference. Possible transformations may include log-transformations. Point estimates and CIs for EC_{50} will be presented after their transformation back to their original scale. If any transformation is applied for the EC_{50} , the transformation will be presented in [Table 19](#).

Otherwise, if a linear model is fit for the response outcome measure and exposure parameter, the following null hypothesis will be tested:

$$H_0: \beta = 0.$$

Furthermore, if a polynomial model is fit for the response outcome measure and exposure parameter, then the following null hypothesis will be tested:

$$H_0: \beta_a = 0.$$

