9.7.1 Sample Size

Table 3: Sample Size/Probability Estimates

Number of Tests	R ²	Proportion of Tests with Specified R ²	Power									
			N=100	N=90	N=80	N=75	N=70	N=65	N=60	N=55	N=50	N=45
24	0.2	0.05	0.95	-	0.88	0.84	0.80	0.78	0.72	0.66	0.6	0.52
48	0.2	0.05	0.95	-	0.88	0.84	0.81	0.76	0.69	0.63	0.56	0.49
176	0.2	0.05	-	0.93	0.88	0.85	-	-	-	-	-	-
24	0.2	0.10	0.97	-	0.92	0.89	0.86	0.83	0.77	0.72	0.65	0.58
48	0.2	0.10	0.98	-	0.92	0.90	0.87	0.84	0.79	0.73	0.66	0.58
176	0.2	0.10	-	0.96	0.92	0.90	-	-	-	-	-	-

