[Implementation Note: Model Type will be either Emax, Linear, Polynomial, or Proportional Odds (for BCS only). Covariates Included in the Model will at minimum include Exposure Parameter, but may also include Sex, Weight Group, Receipt of IV Artesunate or Other Artemisinin-Based Therapy Before Enrollment, Receipt of Concomitant Medications, Receipt of Oral ACT, and Actual Time of Response Measurement. If a polynomial model is fit, all powers included in the model will be listed (e.g., Exposure, Exposure², Exposure³). If an Emax model is fit, Covariates Included in the Model will list any covariates included for each model parameter, e.g. “Exposure; Emax: Sex, Weight”).

Response Transformations Performed will display any transformations to the response variable, such as “Log-transformation”. If no response variable transformation was necessary for the model, Response Transformations Performed will be displayed as “-“.

Parameter Transformations for Inference is only applicable for Emax models. All other model types will have “NA” for this column. For Emax models, this will either be displayed as “-“ if no transformation was necessary, or the parameter and transformation will be displayed, e.g., “EC₅₀: log-transformation”.]

Marker of Physiological Dysfunction	PK Exposure Parameter	Timepoint	Model Type	Covariates Included in the Model	Response Transformations Performed	Parameter Transformations for Inference
PD Analysis Population						
Temperature (°C)	AUC ₀₋₁₂	24 hours post-first IV artesunate dose (N=X)				
		48 hours post-first IV artesunate dose (N=X)				
		Time of completion of planned IV artesunate dosing (N=X)				
		Time of first hospital discharge (N=X)				
	C _{max}	24 hours post-first IV artesunate dose (N=X)				
		48 hours post-first IV artesunate dose (N=X)				
		Time of completion of planned IV artesunate dosing (N=X)				

Table 19: Model Specifications for Assessments of Relationships between Markers of Physiological Dysfunction and Exposure Parameters by Marker of Physiological Dysfunction, Exposure Parameter, Timepoint, and Analysis Population (continued)

		Time of first hospital discharge (N=X)				
T_{max}	24 hours post-first IV artesunate dose (N=X)					
	48 hours post-first IV artesunate dose (N=X)					
	Time of completion of planned IV artesunate dosing (N=X)					
	Time of first hospital discharge (N=X)					
$t_{1/2}$	24 hours post-first IV artesunate dose (N=X)					
	48 hours post-first IV artesunate dose (N=X)					

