If Emax models with no fixed covariates, linear models, or polynomial models are fit, this figure will have two panels with labels “PD Analysis Population (N=X)” and “PD Analysis Population, No Prior IV Artesunate or Other Artemisinin-Based Therapy Subset (N=X)”. If Emax models with fixed covariates on any of the model parameters are fit, then there will be one curve for every combination of fixed covariate levels for each population or subset. These may be displayed in separate panels to facilitate readability, with at most one panel per covariate level combination. For example, if an Emax model is fit with the Emax parameter fit on fixed covariates of sex and weight, the figure could have up to 8 panels with labels “Males <20 kg - PD Analysis Population (N=X)”, “Males <20 kg - PD Analysis Population, No Prior IV Artesunate or Other Artemisinin-Based Therapy Subset (N=X)”, etc.

[figure not shown]
If an Emax model is fit for the given response, exposure, and timepoint, similar plots will be displayed with actual values plotted as points and predicted values plotted as a curve for each combination of fixed covariate levels. The fitted model with estimates of Emax, EC50, E0, and the Hill parameter for each grouping of fixed covariates and analysis population or subset will be displayed in the corresponding panel.

Units will be added to all axes. At minimum, the fitted line given below the plot will have covariates for exposure, but may also have sex, weight group, receipt of IV artesunate or other artemisinin-based therapy before enrollment, receipt of concomitant medications, and actual time of measurement included as covariates. The footnote will be updated to reflect which covariates are included.

Note that models for the No Prior IV Artesunate or Other Artemisinin-Based Therapy Subset will be of the same form as that for the PD Analysis Population, but will only include the subset of covariates included in the model for the PD Analysis Population with effects that remain estimable in the No Prior IV Artesunate or Other Artemisinin-Based Therapy Subset. The footnote will be updated to only include the covariates included in the model.]

$$y=44.5-0.0061x-0.159t-0.273s+0.554w-0.139p-0.0397c$$

$$y=35.3+0.00947x-0.0994t-0.0643s+0.381w-0.0851c$$

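### The fallback linear and polynomial primary models are coded without an intercept, so the exposure test can be invalid whenever no categorical covariate is kept

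*SAP*

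**What the plan says.** SAP 8.1 tests each of ten continuous markers against four exposure parameters at four timepoints. Emax is the first choice; linear or polynomial models are considered where Emax assumptions look unlikely to hold. The SAP supplies PROC GLM code that will be used to fit these models and extract the exposure p-value:

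- Linear: "model resp = baseresp exposure othercovars / noint ss3"
- Polynomial: "model resp = baseresp exposure... exposurea othercovars / noint ss3"

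The written equations contain no constant either. They show baseline with an implied coefficient of 1, whereas the code estimates a baseline slope.

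On covariates, Section 8 states: "All model-based primary and secondary PD analyses will adjust for a subset of the following covariates". Section 8.1 adds that exploratory plots "will be used to inform what subset of covariates will be included in each model". The implementation note to Table 19 reads: "Covariates Included in the Model will at minimum include Exposure Parameter, but may also include Sex, Weight Group". Measurement time, the other optional term, is continuous.

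The sensitivity analysis in children with no prior artemisinin therapy refits the same model form. Its covariates "will be those included in the respective primary analysis model with effects that remain estimable in the sensitivity analysis subset".

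The sample equation for Figure 35, "y=44.5-0.0061x-0.159t-0.273s+0.554w-0.139p-0.0397c", shows a constant and categorical terms but no baseline term.

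**The concern.** In PROC GLM, NOINT removes the constant column. A CLASS covariate puts it back, because its level indicators sum to one for every child. Whether the exposure test is valid therefore depends on an unrelated, data-driven choice: whether any categorical covariate is kept.

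The plan allows none to be kept, by two routes:

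- The plots lead to a primary model with baseline and exposure only, or with measurement time added.
- The primary model keeps prior artemisinin therapy as its only CLASS covariate. That effect is not estimable in the no-prior-therapy subset, so it drops out and the sensitivity model has no constant.

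The line relating response to baseline is then forced through the origin. Regression to the mean alone gives that line a non-zero intercept, and exposure absorbs part of it. A change unrelated to DHA could be reported as an exposure-response relationship in a study meant to inform dosing.

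**Working it through.** **The plan's own figure.** SAP Table 3 ("Sample Size/Probability Estimates") states average power of 0.85, 0.88 and 0.93 at N=75, 80 and 90 for 176 tests, R² 0.2 and 5% non-null. Simple linear regressions *with* an intercept, under Benjamini-Hochberg at 0.05, give 0.854, 0.883 and 0.929. Across the table, 41 of 42 cells agree within two points; the exception is 48 tests, 5% non-null, N=45 (0.468 against 0.49). The power statement is sound and corresponds to models with an intercept.

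**Scope.** 10 continuous markers × 4 exposures × 4 timepoints = 160 tests can be affected, but only where a linear or polynomial model replaces Emax. The Emax models have a baseline parameter E0, and the 16 BCS tests have cumulative-logit intercepts. Neither is affected.

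**Mechanism.** Let the truth be response = c + δ·baseline + error, with no exposure effect and exposure P independent of baseline. Here δ = r·SD(response)/SD(baseline) and c = mean(response) − δ·mean(baseline). With k_B and k_P the CVs of baseline and exposure, the no-intercept fit gives P a large-sample coefficient whose value at mean exposure is

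spurious effect = c × f, where f = k_B² / [(1 + k_B²)(1 + k_P²) − 1].

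It is zero if c = 0 (a purely proportional change) and small if baseline hardly varies. The documents give no marker means, SDs or exposure CV, so the inputs below are assumptions. At k_P = 0.5:

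| Marker: baseline mean (SD) to response mean (SD), r | δ | c | k_B² | f | c × f |
|---|---|---|---|---|---|
| Lactate 4 (2.5) to 2.2 (1.0), 0.3 | 0.12 | 1.72 | 0.391 | 0.529 | 0.91 mmol/L |
| Bicarbonate 18 (4) to 21 (3), 0.4 | 0.30 | 15.6 | 0.0494 | 0.158 | 2.5 mmol/L |
| Hemoglobin 8 (2.2) to 7.5 (2.0), 0.8 | 0.727 | 1.68 | 0.0756 | 0.220 | 0.37 g/dL |
| Temperature 38 (1.0) to 37 (0.6), 0.2 | 0.12 | 32.4 | 0.00069 | 0.0028 | 0.09 °C |

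For lactate, for example: 0.391/(1.391 × 1.25 − 1) = 0.529, and 1.72 × 0.529 = 0.91.

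**Null rejection at nominal 5%.** Settings: N=75, lognormal exposure with CV 0.3, 0.5 and 0.8, 3000 runs per cell. Inputs are the table rows plus lactate 4 (2.5) to 2.2 (1.2), r 0.6, and 3.5 (1.5) to 2.0 (1.0), r 0.6; bicarbonate 18 (4) to 20 (3), r 0.6, and 19 (3) to 21 (3), r 0.7; hemoglobin 8 (2.2) to 7.5 (1.8), r 0.7, and 8 (2.0) to 7.3 (2.0), r 0.9; temperature as in the table with r 0.4.

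| Fit | Lactate | Bicarbonate | Hemoglobin | Temperature |
|---|---|---|---|---|
| Linear, NOINT, no CLASS | 21-100% | 14-99% | 5-87% | 6-10% |
| Quadratic, NOINT, no CLASS, highest power tested | 24-98% | 23-100% | 5-89% | 6-41% |
| Linear, NOINT, time only (21 h, SD 3, assumed) | 5-14% | 7-44% | 5-15% | 5-10% |
| Linear, NOINT, one CLASS covariate | 4-6% | 4-6% | 4-6% | 4-6% |
| Intercept, linear or quadratic | 4-6% | 4-6% | 4-6% | 4-6% |

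A purely proportional change under NOINT also gives 4-6%. In scale-free terms (baseline CV 0.2-0.6), c divided by the residual SD of 0, 1 and 2 gives 4-6%, 7-95% and 13-100%. At N=46, the linear no-CLASS fit gives 14-100% for lactate and 10-91% for bicarbonate.

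**Family level.** 176 tests, of which 9 are non-null (0.05 × 176 = 8.8) with R² 0.2, N=75. The false discovery rate is 0.05 with no defective model. It is 0.05-0.16 with one defective null model, 0.06-0.37 with four and 0.07-0.52 with eight.

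**The case against.** The failing case needs several things to coincide: Emax is abandoned, no CLASS covariate survives, the conditional intercept is non-zero, and nobody acts on the fit. Section 8 says models will adjust for a subset of four covariates, all categorical, and the natural reading is at least one. Weight group sets the dose per kilogram and is an obvious one to keep. All the sample equations in Figures 35 to 38 carry categorical terms and a constant. The Table 19 minimum omits even baseline, so it is not a complete model specification.

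The SAP also permits fit statistics to assist covariate selection. Under NOINT any CLASS covariate restores the constant, so selection tends to bring one in where the defect is worst. Letting AIC add the best of four pure-noise two-level covariates cut the linear rejection rates to 5-23% for lactate, 4-8% for bicarbonate, 5-13% for hemoglobin and 4-6% for temperature. Finally, the inputs are assumed, the runs use untransformed responses, the second route touches only a sensitivity analysis, and the study is declared hypothesis-generating.

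Much of this stands. It makes the failure less likely, and the number of affected models cannot be known from the documents. It does not remove the failure. Nothing requires a CLASS covariate or an intercept. Use of fit statistics is optional, and under BIC one lactate setting still rejected in up to 52%. Residual plots are planned, but no check of the intercept is. A log-transformed response has its own conditional intercept, so transformation is not in itself a cure. Time as the only covariate is not dependable either: up to 44% under the inputs above, 4-11% under another plausible set.

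**Conclusion.** The concern holds. As written, the code for the fallback primary models gives a valid exposure test only if a CLASS covariate is kept or the regression on baseline truly passes through the origin, and the plan ensures neither. Where both fail, the false-positive rate can be far above 5% for markers with a variable baseline and regression to the mean, and near nominal for temperature in the linear model. One such model can be enough to lift the false discovery rate above 0.05, though at the low end of the range it does not.

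The mechanism is certain. The size rests on assumed marker distributions and exposure CVs, and on an unknown number of models without a CLASS covariate. NOINT has no offsetting benefit: with a CLASS covariate it leaves the exposure test unchanged, and without one it can invalidate it. Because this is code for primary-outcome p-values, it should be corrected before it is used.

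**What to change.** - Delete NOINT from both PROC GLM calls in SAP 8.1.
- Write the models as response = intercept + δ·baseline + β·exposure (or its polynomial terms) + η·X + error, with δ estimated, so that the equations match the code.
- Add the baseline term to the fitted equations displayed for the continuous markers (Figures 35 to 194).

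The cost is two words of code, an edit to two equations and to the figure templates, and at most one degree of freedom per model. Where a CLASS covariate is kept, the exposure test does not change. The power in Table 3 stands, since models with an intercept reproduce it.

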In the above model, $\tau_k(P_i, t_i, BCS_{0,i}, X_i) = \Pr(BCS \leq k | P_i, t_i, BCS_{0,i}, X_i)$ represents the cumulative probability that BCS will be less than or equal to $k \in \{0,1,2,3,4,5\}$ given the covariates. The BCS level-specific intercept is represented by α_k , P_i is the exposure parameter value for the i th participant, t_i is the actual response measurement time post-first dose, $BCS_{0,i}$ is the baseline BCS for the i th participant, and X_i are the values for the i th participant of the additional covariates included in the model. The β_1 , β_2 , and η are model parameters associated with the above covariates. The term b_i represents a participant-specific random intercept, where it is assumed that b_i follow a normal distribution with mean zero and nonzero variance. For 24 hours and 48 hours post-first dose timepoints, t_i will be measured in hours post-first dose rounded to the nearest tenths place. For time of completion of the final planned dose of IV artesunate and time of first hospital discharge timepoints, t_i will be measured in days post-first dose rounded to the nearest tenths place.

The following pseudocode will be used to fit the proportional odds mixed effects models for BCS and to extract the p-value for the exposure model parameter.

```
/* Proportional odds model fit and output p-values */
proc glimmix data=dataset(where=(population=p and response=r));
*catvar = any categorical covariates included in the model;
*refvalues = the value(s) to be used as the reference level for categorical
covariate(s);
class catvar(ref=refvalues);
*baseresp = response at baseline;
*othercovars = any other covariates (including those specified in the class statement)
included in the model;
model resp = baseresp exposure time othercovars / dist=multinomial link=cumlogit;
random intercept;
by timepoint;
ods output Tests3=tests3;
run;
data tests3; set tests3(where=(effect='EXPOSURE')) ;
rename ProbF=pval;
run;
```

For the continuous primary outcome response variables, if model assumptions hold, Emax models will be fit for each primary outcome effect and each exposure parameter at each timepoint. The Emax model for primary outcome effect, E_i , is defined as follows:

$$E_i = E_{0,i} + \frac{E_{max} \times P_i^\gamma}{EC_{50}^\gamma + P_i^\gamma} + e_i,$$

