where E_i represents the given response outcome measure for the i th participant at the given timepoint, $E_{0,i}$ is the baseline response outcome effect for participant i , E_{max} is the maximum effect, EC_{50} is the exposure at half-maximal effect, P_i is the exposure parameter value for participant i , γ is the Hill parameter [7, 8] or slope coefficient, and e_i are the measurement errors for participant i . These measurement errors are assumed to be independent and normally distributed with mean zero and nonzero variance. E_{max} , EC_{50} , and $E_{0,i}$ may be modeled with fixed covariate effects, i.e., $E_{max} \sim X_i$ where X_i are the subset of covariates included for E_{max} . The subset of covariates included may differ between E_{max} , EC_{50} , and $E_{0,i}$. Alternatively, E_{max} , EC_{50} , and $E_{0,i}$ may be considered random effects if fixed effects are not included. For example, $E_{0,i}$ may also be modeled instead with a random effect, whereby an additive random component with mean-zero normal distribution will be assumed for $E_{0,i}$ such that $E_{0,i} = E_0 + b_{1i}$, where E_0 , is the population-level quantity and b_{1i} are independently normally distributed random effects with mean zero and nonzero variance. Model selection will proceed in a forward direction from least complex model (no fixed covariates included on any of the above parameters) to more complex. Estimated log-likelihood statistics or other convergence criteria will be used to assist in Emax model selection.

If Emax models are fit for a primary outcome effect, the following pseudocode will be used for model fitting and to extract p-values for the exposure model parameter

```

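### For Emax fits the SAP tests EC50 = 0, which is not the stated null of no exposure effect, yet the p-value enters the primary Benjamini-Hochberg set as if it were

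*SAP*

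**What the plan says.** Protocol 11.1 and SAP Section 5 frame the primary objective as a series of tests, each with the null that exposure has no effect on the marker. SAP Section 5 counts 176 of them: eleven markers, four exposure parameters and four timepoints.

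For the continuous markers, SAP Section 8.1 makes Emax the first choice: "if model assumptions hold, Emax models will be fit for each primary outcome effect and each exposure parameter at each timepoint". The fallback is: "If Emax model assumptions seem unlikely to hold, linear or polynomial models will be considered as informed by the exploratory scatterplots". In the Emax equation EC50 "is the exposure at half-maximal effect", Emax is the maximum effect and gamma "is the Hill parameter". Emax, EC50 and the baseline term "may be modeled with fixed covariate effects".

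On testing: "If an Emax model is fit for the response outcome measure and exposure parameter, the following null hypothesis will be tested". The printed null is EC50 = 0. EC50 may first be transformed towards normality, and a log transformation is named. For polynomial fits only the coefficient of the highest power, beta_a, is tested.

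On computation: "If Emax models are fit for a primary outcome effect, the following pseudocode will be used for model fitting and to extract p-values". The code ends under the comment "Mean and Standard Deviation of EC50, for example", with a posterior mean and SD. It gives no test statistic and passes no prior.

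Section 8.1 then treats all the resulting p-values as tests of the effect of exposure and puts them through Benjamini-Hochberg at 0.05. The result decides the significance marks in Tables 17 and 18.

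**The concern.** EC50 says where along the exposure axis the response changes. Emax says whether and how much it changes. A null on EC50 therefore does not ask the primary question.

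Benjamini-Hochberg controls the false discovery rate only if the p-values of true nulls are valid. If EC50 p-values are mixed with slope p-values from linear fits and proportional-odds p-values for the Blantyre Coma Score (BCS), one family holds different hypotheses. A mark in Table 17 or 18 then need not mean an exposure effect, and an unmarked cell need not mean that none was detectable. The Table 3 powers were simulated for simple linear tests, so they do not describe the Emax branch.

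**Working it through.** **1. How many tests.** BCS always uses proportional odds: 1 x 4 x 4 = 16 tests. The ten continuous markers give 10 x 4 x 4 = 160, and 160 + 16 = 176. So 160 is the ceiling for Emax.

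**2. Table 3 reproduced.** I simulated independent simple linear regressions with two-sided t-tests, Benjamini-Hochberg at 0.05, 5000 runs per cell. With 176 tests, R^2 = 0.2 and 5% non-null (9 tests), average power is 0.928, 0.885 and 0.851 at N = 90, 80 and 75. Table 3 prints 0.93, 0.88 and 0.85. All 26 cells checked agree within 0.02.

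**3. Algebra.** The model is E = E0 + Emax x P^gamma / (EC50^gamma + P^gamma) + error.
- With Emax = 0 the mean is E0 for every EC50. EC50 drops out of the likelihood and is not identified.
- With EC50 = 0 the mean is E0 + Emax, also flat in P. This is one flat case, on the boundary of the allowed range.

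So no effect does not imply EC50 = 0, and rejecting EC50 = 0 does not show an effect.

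**4. Log scale.** EC50 = 0 has no finite logarithm. A back-transformed interval exp(a ± 1.96 s) lies above zero for every data set.

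**5. What the prior alone gives.** The code supplies only a mean and an SD, so I take z = mean/SD as the test (my assumption). With a flat likelihood the posterior is the prior:
- uniform from 0 to any limit: z = sqrt(3) = 1.73, p = 0.083
- lognormal with log-SD 0.3: z = 1/sqrt(exp(0.09) - 1) = 3.26, p = 0.001

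**6. Single tests at 0.05.** N = 75; assumed lognormal exposure with CV 50%, Hill = 1, no covariates. The effect case is a true Emax curve with R^2 = 0.2.

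| Assumed EC50 prior (raw scale) | Rejects, no effect | Rejects, effect |
|---|---|---|
| Uniform to 5 x median exposure | 4.8% | 30% |
| Half-normal, scale 2 x median | 0.0% | 5.2% |
| Truncated normal at median, SD 2 x median | 0.1% | 7.6% |
| Truncated normal at median, SD 0.5 x median | 34.3% | 94.3% |
| Lognormal at median, log-SD 1 | 0.0% | 0.0% |
| Least-squares fit, Wald test of EC50 = 0 (no prior) | 0% | 0% |
| Maximum-F test of a flat curve, permutation p-value (no prior) | 3.4% | 98.9% |

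**7. Effect on the family.** N = 75, 176 tests, 9 non-null, 2000 runs; Emax assigned at random to 25%, 50% or 100% of the 160 eligible tests.
- All linear: power 0.85, FDR 0.046.
- Raw-scale EC50 test, three of the priors: power about 0.64, 0.44 and 0.06, FDR at most 0.036.
- Log scale read as log EC50 = 0 (EC50 equal to one unit), median exposure 1000: FDR 0.82, 0.90 and 0.94. At median exposure 2 the same reading gives power 0.64, 0.43 and 0.06, so the result depends on the measurement unit.

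A further simulation used Emax only where AIC preferred it to a linear fit, as a stand-in for the SAP's visual choice. It used exposure CV 30-80% and six priors. AIC chose Emax in 2-8% of no-effect and 30-70% of effect data sets. Average power for continuous markers was 0.19-0.56 with FDR 0.03-0.06 under five priors. Under the lognormal log-SD 0.3 prior it was 0.89-0.95 with FDR 0.27-0.60. These figures are rougher: a valid log-slope test in the same runs showed FDR 0.03-0.07, where theory gives 0.05 x 167/176 = 0.047.

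**8. Polynomial branch.** The hypothesis beta_a = 0 says only that the highest power is not needed. It leaves beta_1 to beta_(a-1) free, so it is not the no-effect null either.

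**The case against.** The strongest case against a severe reading has four parts.

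*The study is exploratory and transparent.* Section 5 calls it hypothesis-generating. Table 19 reports model type and transformation, and the notes to Figure 35 onwards require the data to be shown with fitted Emax, EC50, E0 and Hill. A careful reader could notice a misleading mark. That stands as mitigation, but it supplies no valid p-value, and the SAP still claims FDR control at 0.05.

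*Emax is gated.* It is used only if its assumptions appear to hold. A reader might infer that all 160 tests are affected; the documents do not support that. The number is unknown until the plots are seen.

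*The large FDR figures are built in.* A reader might infer that the trial's false discovery rate will be 0.27-0.94. Those figures arise only under a tight prior that I assumed, which rejects before any data (z = 3.26), or under a log EC50 = 0 reading that the SAP does not state. The code passes no prior, so package defaults would apply, and the documents do not give them.

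*The polynomial contrast can be overstated.* Under a linear truth with R^2 = 0.2 and N = 75, beta_a alone rejects 5% and the joint test 92-95%. In that situation the SAP could choose the linear branch, whose null is correct. The contrast shows the fault, not its expected size.

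None of this touches the mismatch between the stated null and the tested one. No section adds a test of Emax = 0 or of a flat curve.

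**Conclusion.** The plan is wrong as written and should be corrected before the analysis. The conclusion rests on the SAP's own definitions and the algebra in step 3, not on the simulations. For every Emax fit the p-value does not test the stated primary null, so neither the 0.05 FDR claim nor the Table 3 power covers it. The polynomial branch shares the fault in a milder form.

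The size cannot be fixed from the documents. It depends on the unstated prior, the scale used for EC50 and how often Emax is chosen. In most raw-scale settings tried the harm is lost power. Inflated false discovery is possible but is shown only under the special assumptions named above. All simulated figures are illustrations resting on assumed priors, exposure distributions, Hill = 1 and independent tests.

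**What to change.** Change SAP Section 8.1 as follows.

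- **Emax fits.** Compare the fitted Emax model with the covariate-matched model that has no exposure term. Set all Emax coefficients, including covariate effects on Emax, to zero under the null; maximise the statistic over EC50 and Hill; and take the p-value from a covariate-preserving (Freedman-Lane) permutation reference. The smallest p-value from B permutations is 1/(B + 1). For a lone signal to pass 0.05/176 = 0.00028, B must be at least 176/0.05 - 1 = 3519.
- **Polynomial fits.** Test beta_1 = ... = beta_a = 0 jointly.
- **EC50.** Report it with its interval, and state the prior, but give it no p-value or significance mark. Footnote Tables 17 and 18 to say which test each p-value comes from.

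An acceptable simpler option is one pre-specified, covariate-adjusted slope test of exposure for every continuous marker, with the exposure scale fixed before response data are analysed.

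**Cost.** SAP wording, table footnotes and modest computing; no new data. A covariate-bearing version of the flat-curve test (199 permutations, 2000 replicates) held its level, at 4.0% for N = 75 and 5.6% for N = 46. It has somewhat less power than a well-scaled slope test: 95% against 98% at N = 75, and 77% against 88% at N = 46, the number enrolled at the end of the planned period.

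The slope test loses Benjamini-Hochberg power when its scale is wrong in either direction (N = 75, 9 of 176 non-null, exposure CV 30/50/80%):
- linear truth: log exposure 0.82/0.76/0.64, untransformed 0.84/0.82/0.77
- Emax truth: untransformed about 0.83/0.79/0.67, log exposure 0.85

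A log-exposure slope therefore does not match Table 3 in general. A slope test can also miss a non-monotone relationship. For these reasons the flat-curve comparison should be the first choice.
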